### 8.3.4 Other Analyses/Assessments

#### Exploratory Analysis:

- We will record rates of adverse pathologic features including rates of positive margins, LVI, and pathologic upstaging (e.g., by T or N status) as compared to clinical staging based on pre-operative scans, for comparison to historical controls.
- We will perform RNA sequencing and whole exome sequencing analysis on isolated cancer cell populations from pre-treatment tumor biopsy specimens, as well as tumor tissue acquired at the time of surgical resection (post-osimertinib). Gene Set Enrichment Analysis will be performed to identify osimertinib-induced changes in common cancer related pathways, including: RAS-RAF-MAPK, PI3K-AKT, WNT-  $\beta$  catenin, JAK-STAT, HGF-MET, and IGF-1R, as well as emerging pathways of resistance (i.e. NF- $\kappa$ B and Hippo-YAP) [1, 46, 47]. We will determine whether there is a statistically significant increase in oncogenic/survival pathway related gene expression signatures in the post-osimertinib compared to the pre-treatment sample using established methods [48]. We will compare MPR rates in tumors that exhibit specific oncogenic/survival pathway activation post-osimertinib treatment compared to tumors that do not. IHC analysis will be performed on pre-treatment and post-surgical specimens to confirm pathway activation identified by transcriptional analysis (i.e. phosphorylated-ERK (indicative of MAPK signaling), phosphorylated-AKT (indicative of PI3K signaling) or nuclear NF- $\kappa$ B (RELA), or -  $\beta$  -catenin expression). Samples will be scored in a continuous manner and difference among time points will be determined by a two-tailed T-test.
- We will assess for shifts in the cellular make-up of the tumor microenvironment induced by osimertinib treatment by performing single cell dissociation and fluorescence associated cell sorting (FACS) on fresh pre-treatment tumor biopsies and post-osimertinib tumor resection specimens. Using FACS gating strategies established and validated by the [name] lab at UCSF [49], we will isolate CD45+ immune cells and determine how osimertinib treatment alters the proportions of cells that make up the lymphoid (CD4+ and CD8+ T cells, Tregs, NK cells, B cells) and myeloid (macrophages, neutrophils, mast cells, dendritic cells) compartments. We will then use RNA-Seq to assess the transcriptional profiles of populations of TAMs, CD4+ and CD8+ T Cells (**Fig. 5**). We hypothesize that osimertinib treatment will induce a pro-tumor immune microenvironment that allows for tumor cell persistence. Specifically, we will assess the polarization of TAMs by assessing the mRNA expression profiles of genes classically associated with TH1-skewed (i.e. *TNF- $\alpha$* , *IL-6*, *IL-12p40*, and *IL-1 $\beta$* , and *Nos2*) and TH2-skewed polarization (i.e. *ARG1*, *TGFB*, *CD163*, *CD206*), many of which are targets of NF- $\kappa$ B transcriptional activation[50]. We will also investigate whether osimertinib affects

T-cell phenotypes. CD4+ T cells will be assessed for the expression of genes indicative of TREG, TH1, TH2, or TH17 activity (i.e. *GATA3*, *T-bet*, *FOXP3*, *IFN $\gamma$* , *IL-4*, *IL-13*, *IL-10*, and *IL-17a*)[50], and CD8+ T cells will be assessed for expression of cytotoxic effector molecules (*IFN $\gamma$* , *GRZA*, *GRZB*, and *PRF1*)[50]. Finally, tumor cells and infiltrating immune cells will be assessed for shifts in PD-1 and PD-L1 expression (by RNA-Seq and IHC), a phenomenon that has been linked to NF-kB activity[41], and which may indicate changes in anti-tumor immunity induced by osimertinib. Comparisons will be made to PBMCs when possible. Assessment of TIL and TAM infiltration into the tumor microenvironment, and of TAM polarization will be confirmed by IHC analysis for relevant macrophage attributes including CD68, CD163, CD206, iNOS, HLA-DR, as well as for CD4, CD8, and PD-L1, as well as for cancer-associated fibroblasts. Comparisons will be made to PBMCs when possible. Samples will be scored in a continuous manner and difference among time points will be determined by a two-tailed T-test.

- We will assess peripheral blood samples for ctDNA analysis. Descriptive statistics and graphical methods will be used to analyze the data.

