##### 1.4.1 Exome and transcriptome sequencing

We will perform RNA sequencing and whole exome sequencing analysis on isolated cancer cell populations (Fig. 5) from pre-treatment tumor biopsy specimens, as well as tumor tissue acquired at the time of surgical resection (post-osimertinib). Gene Set Enrichment Analysis will be performed to identify osimertinib-induced changes in common cancer related pathways, including: RAS-RAF- MAPK, PI3K-AKT, WNT-  $\beta$ -catenin, JAK-STAT, HGF-MET, and IGF-1R, as well as emerging pathways of resistance (i.e. NF- $\kappa$ B and Hippo- YAP) [1, 46, 47]. We will determine whether there is a statistically significant increase in oncogenic/survival pathway related gene expression signatures in the post-osimertinib compared to the pre-treatment sample using established methods [48]. We will compare MPR rates in tumors that exhibit

**Figure 5. Schema of tumor and immune cell isolation strategy.** Pre-treatment tumor biopsies and post-surgical specimens will undergo single-cell dissociation and FACS analysis to isolate tumor cells CK+CD45+CD31+, CD4+ and CD8+ T-cells, and Tumor Associated Macrophages (TAMs). Exome and RNA sequencing will be performed

specific oncogenic/survival pathway activation post-osimertinib treatment compared to tumors that do not. Immunohistochemistry (IHC) analysis will be performed on pre-treatment and post-surgical specimens to confirm pathway activation identified by transcriptional analysis (i.e. phosphorylated-ERK (indicative of MAPK signaling), phosphorylated-AKT (indicative of PI3K signaling) or nuclear NF- $\kappa$ B (RELA), or beta-catenin expression).

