## 2.3 Exploratory

- To evaluate long-term measures of efficacy in patients treated with osimertinib neoadjuvant therapy.
- To explore tissue and cell-free biomarkers that may be predictive of response or primary resistance to osimertinib neoadjuvant therapy.

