### 8.3.2 Primary Analysis (or Analysis of Primary Endpoints)

MPR rate (primary endpoint) will be determined in patients who receive at least one dose of study drug.

Patients who receive one dose of study drug and become ineligible for surgery either because of disease progression or adverse event will be deemed not to have achieved MPR.

In patients who undergo surgical resection or their lung tumor resection specimens will be processed at the local institution following CAP and CLIA guidelines. Immediate sampling of the tumor and overnight fixation in 10% buffered formalin for paraffin embedding, usually within 20-24 hours after fixation. For histopathological evaluation, at least one sample per every 1-cm of diameter will be submitted for FFPE processing and pathology analysis. The local institutional study pathologist will assess each case for MPR, using percentage of viable tumor cells (cutoff as + MPR is  $\leq 10\%$  of viable tumor cells) as has been reported [24]. The pathological response should be reported as average percentage of viable tumor cells by slide examined.

Pathology slides (H&E and IHC and special stains) will be forwarded to the designated central pathologists for the study and MPR will be determined as described above.

In order to more fully evaluate the specimens associated with this trial, the central review pathologists will score the material using criteria as follows:

Pathological CR: Residual viable tumor: 0% MPR: Residual viable tumor:  $\leq 10\%$

Pathological response (not meeting major response criteria) 11-49% residual viable tumor. No pathological response: 50% or greater residual viable tumor.

Predominant reaction type: Necrosis, Fibrosis

**Tumors that exhibit  $\leq 10\%$  viable tumor will meet the criteria for an MPR as has been previously described [24].** The MPR rate will be reported with 95% confidence intervals.

As needed, a sub-set of tissues will be independently evaluated by both pathologists for assessment of inter-pathologist reproducibility for this scoring.

Whenever possible, the following will be included:

- Concurrent submission of pre-treatment biopsy or FNA sample. This can help inform pathologic evaluation in that pre-treatment necrosis can be assessed, within the context of potential sampling bias.
- Whenever feasible, all post-treatment surgical tumor samples will be submitted for pathologic examination (full lesion block-in), after tissue procurements have been completed.

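### MPR is compared by pathway activation read on residual cancer cells, so which tumors can be classified depends on MPR itself; the plan needs a baseline comparison and a rule for unassessable tumors

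*Combined protocol and SAP*

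**What the plan says.** Section 8.3.4, under the exploratory analyses, describes the assay and then the comparison. The assay: "We will perform RNA sequencing and whole exome sequencing analysis on isolated cancer cell populations", taken from the pre-treatment biopsy and from the resection. The legend to Figure 5 in section 1.4.1 gives the isolation step: "Pre-treatment tumor biopsies and post-surgical specimens will undergo single-cell dissociation and FACS analysis to isolate tumor cells". The comparison: "We will compare MPR rates in tumors that exhibit specific oncogenic/survival pathway activation post-osimertinib treatment compared to tumors that do not". Immunohistochemistry has a supporting role: "IHC analysis will be performed on pre-treatment and post-surgical specimens to confirm pathway activation identified by transcriptional analysis".

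The outcome is defined by how much viable tumor remains. Section 8.3.2 sets MPR at 10% viable tumor or less, and its central scoring scale begins "Pathological CR: Residual viable tumor: 0" (percent). Section 8.3.3 defines pCR in the same way. Section 8.3.2 also counts patients who become ineligible for surgery through progression or an adverse event as not having achieved MPR. Sections 6.1.2.3 and 6.1.2.6 offer such patients only an optional post-treatment biopsy.

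Section 2.3 gives one exploratory objective as: "To explore tissue and cell-free biomarkers that may be predictive of response or primary resistance to osimertinib neoadjuvant therapy".

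For this comparison the plan gives no minimum cell or tissue requirement, no rule for tumors that cannot be classified and no denominator. A tissue-adequacy condition appears only for xenografts and organoids (section 1.4.3). Section 8.3.4 names no test for it; section 8.3.1 has only a general sentence on univariate tests.

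**The concern.** The grouping variable needs viable cancer cells in the resection, and the outcome is the near-absence of those cells. Whether a tumor can be placed in a group therefore depends on its response. At 0% viable tumor there is nothing to classify. At 1-10% it depends on cell yield, which the documents do not give. At the other end, unresected non-MPR patients also lack a post-treatment specimen unless they take the optional biopsy.

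In addition, activation in the resection is measured at the same moment as MPR. It can describe the tumor that survived treatment, but it does not serve the part of objective 2.3 that asks what predicts response.

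At stake is the reading of the mechanistic result: an apparent link between pathway activation and poor response could be real, diluted or created by how unassessable tumors are handled, and the plan leaves that handling open.

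**Working it through.** **The plan's own figure.** The documents give no figure for this comparison. The nearest is the 87% power in section 8.1.1 (n = 27, 22% versus 50%, 5% level). The exact binomial test rejecting at 11 or more MPRs has type I error 0.022 and power 0.876; the two-sided arcsine approximation gives 0.870. The figure reproduces, and nothing below touches it.

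**Inputs.** From section 8.1.1: N = 27, and MPR rate m = 50% (alternative) or 22% (null). Assumed, because the documents give no pCR rate or cell yield: a share f of MPR tumors cannot be classified (0 to 75%, including every pCR), all 27 patients are resected, and all non-MPR tumors can be classified. Activation frequencies are also assumed.

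**Step 1: who is left.** Assessable n = 27(1 − mf); MPR rate among them = m(1 − f)/(1 − mf).

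| f | n (m = 50%) | MPR rate | n (m = 22%) | MPR rate |
|---|---|---|---|---|
| 0 | 27.0 | 50% | 27.0 | 22% |
| 25% | 23.6 | 43% | 25.5 | 17% |
| 50% | 20.3 | 33% | 24.0 | 12% |
| 75% | 16.9 | 20% | 22.5 | 7% |

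This is the overall rate in the analysed set, not the contrast between groups.

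**Step 2: unassessable tumors dropped, loss depends on MPR status alone.** Let activation be a1 in MPR and a0 in non-MPR tumors. The MPR rate in activated tumors is m(1 − f)a1 / [m(1 − f)a1 + (1 − m)a0]; for non-activated tumors replace a by 1 − a. With m = 50%, a1 = 30% and a0 = 60%:

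- f = 0: 0.15/0.45 = 33% versus 0.35/0.55 = 64%, difference 30 points.
- f = 50%: 0.075/0.375 = 20% versus 0.175/0.375 = 47%, difference 27 points.
- f = 75%: 0.0375/0.3375 = 11% versus 0.0875/0.2875 = 30%, difference 19 points.

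The odds ratio, (0.3 × 0.4)/(0.7 × 0.6) = 0.29, does not involve f. With a1 = a0 = 50% and f = 50%, both groups show 33%: no association stays no association.

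**Step 3: unassessable tumors dropped, loss also tracks activation.** Assume 20% pCR, 30% other MPR and 50% non-MPR, with activation 20%, 40% and 60%. With everyone counted, activated and non-activated MPR shares are 0.16 and 0.34, and non-MPR shares are 0.30 and 0.20, so the odds ratio is (0.16 × 0.20)/(0.34 × 0.30) = 0.31. Dropping pCR gives (0.12 × 0.20)/(0.18 × 0.30) = 0.44. With pCR at 10% or 5% of patients the move is 0.38 to 0.44 or 0.41 to 0.44. An activation frequency in a tumor with no viable cells is notional, so this only shows direction.

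**Step 4: unassessable tumors counted as non-activated, no true association.** With m = 50% and activation 50% in both groups:

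- f = 25%: 0.1875/0.4375 = 43% versus 0.3125/0.5625 = 56%.
- f = 50%: 0.125/0.375 = 33% versus 0.375/0.625 = 60%, odds ratio 0.33.

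**Step 5: unresected patients.** Their loss removes non-MPR cases and so pushes the MPR rates up, against Step 1. Its size is not in the documents.

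**Step 6: precision.** Even with all 27 tumors split 13 to 14, Fisher's exact test at 5% has about 67% power for 25% versus 75%, and about 25% for 22% versus 50%.

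**The case against.** The strongest reply is Step 2. If loss depends only on MPR status, this is sampling by outcome: the odds ratio survives and a null result stays null. That stands. A reader might infer that any association found would merely reflect which tumors had cells left. The documents do not support that without a further condition, either loss related to activation or unassessable tumors coded as non-activated, and section 8.3.4 does not say it will code them so. It does not exclude it either.

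A reader might also infer that MPR tumors as a class drop out. Only pCR is certain. Tumors with 1-10% viable cells still hold cancer cells, section 6.2.3 takes two to four fresh pieces from the resection, and section 1.4.2 allows single-cell sequencing when possible.

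Section 8.3.4 does not call this comparison predictive. Section 2.4.3 lists change between baseline and resection as its own endpoint, and objective 2.3 can also be served by pre-treatment sequencing and ctDNA. So the comparison does not contradict objective 2.3; it leaves the predictive part of it without a stated MPR comparison by baseline pathway status.

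Baseline activation cannot test the hypothesis in section 1.3.1, that NF-κB signaling is switched on by treatment. That also stands, and it is why the post-treatment analysis should stay.

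Immunohistochemistry does not remove the problem. Its stated role is to confirm the transcriptional call, and tumor-cell staining needs residual tumor cells too.

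**Conclusion.** The point holds in a limited form. The comparison in section 8.3.4 is selected on its own outcome: with certainty for pCR, plausibly for tumors with 1-10% viable cells, and in the opposite direction for unresected patients. What follows depends on the loss mechanism and on handling the plan does not state. Under loss by MPR status alone, rates fall and the rate difference narrows (30 to 27 points at 50% loss in the example), with the odds ratio unchanged. If loss also tracks activation, the odds ratio moves (0.31 to 0.44 in the example). If unassessable tumors are counted as non-activated, a false 33% versus 60% can appear with no true association. All these sizes rest on assumed loss and activation frequencies.

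A reader might infer a threat to the trial's main result. There is none: the analysis is exploratory, no decision hangs on it, and the MPR endpoint and its 87% power are untouched. It is worth correcting because the correction is cheap.

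**What to change.** Amend section 8.3.4, and 1.4.1 to match:

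- Add a comparison of MPR by pathway activation in the pre-treatment biopsy, and name it as the one that addresses prediction of response under objective 2.3.
- Keep post-treatment activation to describe within-patient change and the residual tumor, labelled as conditional on residual viable cells. It should stand beside the baseline comparison, since only it bears on treatment-induced activation.
- State that unassessable tumors are never coded as non-activated.
- Report the number assessable in each category: 0%, 1-10%, 11-49%, 50% or more viable tumor, and unresected.

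The cost is analysis-plan wording; section 8.3.4 already sequences the pre-treatment specimens, so no new samples are needed. The downside is that patients with a deferred or inadequate baseline biopsy are not in the baseline comparison. Sections 6.1.1.2 and 6.2.2 allow deferral, 6.2.2 accepts a fine-needle aspirate and treats one core as adequate, and the documents do not say how many patients this affects, so that count should be reported as well.

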**Study Schema:**

**3.2 Number of Participants**

27 evaluable patients will be enrolled in the study.

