### 8.1 Sample Size and Accrual Rate Considerations

#### 8.1.1 Sample Size and Power Estimate

27 evaluable patients will provide 87% power to detect a MPR rate of 50% as compared to a null rate of 22%, at the 5% significance level.

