## 8.3 Analyses Plans

### 8.3.1 Analysis Population

All patients who receive a dose of osimertinib will be analyzed for safety and efficacy. Participants who discontinue from study participation prior to surgical resection may be replaced after discussion with the Study PI.

Demographic and baseline characteristics will be summarized. In general, frequency distribution and percentage will be used to summarize categorical measurements, while mean with standard deviation and median with interquartile range will be used to describe symmetric and skewed continuous measurements, respectively. Univariate analysis among variables will be assessed using the two-sample t-test, Wilcoxon-rank-sum test, or Chi-square test, as appropriate.

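### The exploratory comparison of pathway activation with pathological response uses yes/no on both sides, which at moderate association costs about 20–30 points of power that a rank analysis would keep

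*Combined protocol and SAP*

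**What the plan says.** Section 2.3 sets an exploratory objective: "To explore tissue and cell-free biomarkers that may be predictive of response or primary resistance to osimertinib neoadjuvant therapy". The one stated analysis that relates pathway activation to pathological response is in 8.3.4 (repeated in 1.4.1): "We will compare MPR rates in tumors that exhibit specific oncogenic/survival pathway activation post-osimertinib treatment compared to tumors that do not". It gives no activation threshold, no test and no power.

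Both sides of this comparison have a finer measure behind them, at least in part:

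- **Response.** MPR is a cut: tumors with at most 10% "viable tumor will meet the criteria for an MPR as has been previously described" (8.3.2). The same section, after describing the local pathologist's assessment, says: "The pathological response should be reported as average percentage of viable tumor cells by slide examined". The central review criteria that follow are bands: 0%, at most 10%, 11–49%, and 50% or more.
- **Pathway.** After listing the IHC markers, 8.3.4 says: "Samples will be scored in a continuous manner and difference among time points will be determined by a two-tailed T-test". The continuous scores are thus used for the change over time, not for the link with response.

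Section 8.3.1 gives a general statement on tests: "Univariate analysis among variables will be assessed using the two-sample t-test, Wilcoxon-rank-sum test, or Chi-square test, as appropriate". It is not tied to this comparison. Section 3.2 fixes the size: "27 evaluable patients will be enrolled in the study".

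**The concern.** The 10% cut has a clear purpose in the primary analysis, because the 22% historical rate is expressed on that scale. An association within the trial has no historical rate to match, so that reason does not carry over. Here the cut treats a tumor with 15% viable cells like one with 90%, and the yes/no activation label discards the grading of the marker score.

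Defining mechanisms of incomplete response is a stated reason for the neoadjuvant design (Abstract; 1.3.4). With so few tumors, a comparison that drops information already collected will more often fail to show a moderate association that exists.

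**Working it through.** **1. The plan's own figure.** The documents state power only for the primary test: 87% for 50% against 22% with 27 patients (8.1.1). An exact binomial rule of at least 11 MPRs out of 27 has type I error 2.2% under 22% and power 87.6% under 50%. The rule of at least 10 has type I error 5.5% and is excluded at 5%. The arcsine two-sided form gives h = 2(arcsin√0.50 − arcsin√0.22) = 0.594, and Φ(0.594·√27 − 1.96) = Φ(1.13) = 87.0%. The stated figure reproduces, and nothing below affects it.

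**2. Inputs for the exploratory comparison.**
- From the documents: at most 27 tumors; MPR rate 50% (design) or 22% (null); chi-square and Wilcoxon as listed tests (8.3.1).
- Assumed, because the documents give no value: two-sided 5%; half of tumors activated; percent viable tumor and pathway score as bivariate normal on a latent scale with correlation ρ.

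**3. What ρ means in MPR rates.** With both measures cut at the median, the MPR rate is 1/2 + arcsin(ρ)/π in non-activated and 1/2 − arcsin(ρ)/π in activated tumors. This gives 63% against 37% at ρ = 0.4, 67% against 33% at 0.5, and 70% against 30% at 0.6.

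**4. Simulated power, 27 tumors, MPR 50%, half activated (6,000 trials per row).**

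| ρ | Fisher | Chi-square | Spearman | Loss vs chi-square | Loss vs Fisher |
|---|---|---|---|---|---|
| 0.4 | 20% | 29% | 52% | 23 | 32 |
| 0.5 | 31% | 42% | 72% | 30 | 41 |
| 0.6 | 47% | 59% | 90% | 30 | 43 |

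Losses are from unrounded values. Separate simulations differ by a few points (chi-square loss 20, 28 and 31 in one). Spearman's rejection rate under no association was 4.6% in one simulation and about 5–6% in others, so the gain is not bought with false positives.

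**5. Checks by formula at ρ = 0.5.**
- Two proportions, 13.5 tumors per group: (0.333·√13.5 − 1.96·√(2·0.5·0.5)) / √(2·0.667·0.333) = (1.225 − 1.386)/0.667 = −0.24, so power is 40% (simulated 42%).
- Spearman: the population value is (6/π)·arcsin(0.25) = 0.483; atanh(0.483)·√(24/1.06) − 1.96 = 2.50 − 1.96 = 0.54, so power is 71% (simulated 72%).

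**6. Weak association.** At ρ = 0.2, chi-square has 11% and Spearman 15%. At ρ = 0.3, one simulation gives 17% and 30%; another gives a loss of 11 points. The range is about 5–12 points.

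**7. Only percent viable tumor used in full.** Wilcoxon on percent viable tumor by activation group, against chi-square on MPR: 34% against 28% (ρ = 0.4), 52% against 43% (0.5) and 73% against 60% (0.6), a gain of 6, 9 and 13 points. If activation is truly a step, with 13 and 14 tumors and MPR 30% against 70%, it is 71% against 58%, or about 14 points.

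**8. Other settings.**
- MPR 22%, half activated, ρ = 0.4–0.7: loss 30–45 points against chi-square.
- 22 tumors, MPR 50%, ρ = 0.4–0.7: loss 17–31 points against chi-square.
- Percent viable tumor recorded in 5–10% steps with ties at 0%, ρ = 0.5: chi-square 42%, Spearman 73%.
- 10–20% of tumors with no viable cells and so no score, ρ = 0.5, MPR 50%: chi-square 23–32%, Spearman 41–54%.

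**The case against.** The case for leaving the plan as it is has real weight.

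- **The analysis is exploratory.** It carries no alpha, power claim or decision rule. Comparing rates of the trial's own endpoint is conventional and easy to read, and nothing forbids adding a correlation. This stands and sets the weight of the point.
- **The size depends on assumptions.** No correlation or activated share is in the documents, and Fisher's test is not named. The response comparison in 1.3.3 cannot serve as an anchor: it concerns pre-treatment gene alterations in T790M-positive disease, and its TP53 entry prints 8/13 as 69%, although 8/13 is 62%. This stands, so only a range is given.
- **Full-scale data are not in hand for every pathway.** A reader might infer that they are. The continuous-scoring sentence most naturally covers the IHC markers. The examples listed are for MAPK, PI3K, NF-κB and beta-catenin, and IHC is there to confirm the transcriptional finding. No per-tumor expression score is defined. Central review is specified in bands, so a central numeric percentage is not clearly planned. This stands and limits what can be done without further definition.
- **The remedy is no cure.** At ρ = 0.4 Spearman reaches only about 50%, before any allowance for several pathways. True, but it still does better on the same tumors.

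A reader might also infer that a non-significant result would be reported as no relation. The plan does not say so. What does not stand is that exploratory status is a reason to drop collected information.

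**Conclusion.** The point holds as a modest one. The only stated link between pathway activation and pathological response is a yes/no by yes/no comparison, while percent viable tumor is already reported and the IHC markers are scored continuously.

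At the design MPR rate, with half of tumors activated and an assumed latent correlation of 0.4–0.6, the cost is about 20–30 points of power against chi-square, and up to about 40 if Fisher's test were used. It is about 5–12 points for correlations of 0.2–0.3. Where activation can only be yes/no, about 5–14 points are recoverable. All figures take 27 as the maximum: patients without resection have no surgical specimen, and tumors without viable cells may yield no score.

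A reader might take this as a flaw in the MPR endpoint or the sample size. The documents do not support that: the 10% cut suits the primary comparison with 22%, and the stated 87% power reproduces. This is an optional improvement, not an error affecting the primary conclusion.

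**What to change.** In 8.3.4, and in the matching sentence of 1.4.1:

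- Add as the main exploratory association analysis a Spearman correlation, with 95% CI, between percent viable tumor and the continuous pathway score where one exists. That means the IHC markers, or a per-tumor expression score if the plan defines one.
- Where activation is only yes/no, compare percent viable tumor between the groups by a Wilcoxon rank-sum test.
- Keep MPR rates by activation status as a descriptive table.
- Have central review record the numeric percentage of viable tumor beside its category.

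The primary endpoint and its 10% cut do not change. The cost is a few sentences and one numeric field on the central pathology form, with no new patients, samples or readers. The small downside is that a rank correlation is less directly interpretable than two rates, which is why the table stays.
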